14.5. INSURANCE POLICY

In accordance with the provisions of the law and GCP, the Sponsor Pierre Fabre Medicament has an insurance policy intended to guarantee against possible damage resulting from the research.

The studies and/or experiments performed on behalf of the Sponsor Pierre Fabre Medicament are specifically and expressly guaranteed.

It is advisable to underline that non-compliance with the Research Legal Conditions is a cause for guarantee exclusion.

Unintentional infringements and vicarious liability are covered by our insurance.

14.6. FINANCIAL CONSIDERATIONS

The funding of research is provided by the Sponsor (Investigator fees, study costs, subject compensation for travel expenses, etc.).

By signing the protocol, the Investigator declares no conflicts of interest.

15. ADMINISTRATIVE PROCEDURES

15.1. PROTOCOL AMENDMENTS

Neither the Investigator nor the Sponsor may alter the protocol without the authorization of the other party. All changes to the protocol will be subject to an amendment which must be dated and signed by both parties and must appear as an amendment to the protocol.

Substantial amendments are submitted for approval/authorization to the IEC/IRB and Competent Authorities. Urgent amendments are submitted for approval/authorization to the IEC/IRB and Competent Authorities but may be implemented immediately under specific conditions defined with the Sponsor.

15.2. SOURCE DOCUMENTS, INVESTIGATOR'S FILE STORAGE

The Investigator:

- keeps all trial-related documents in appropriate file folders. Records of subjects, original ICFs, source documents, e-CRFs, treatment inventory, IEC/IRB and Sponsor correspondence pertaining to the study must be kept on file,
- retains all documents relating to the screening (consent and investigation results) of all subjects screened in the trial or not,
- retains a list of the subjects' names, addresses (and/or number of medical file), code numbers, dates of entry into and completion of the trial period, to allow checking of data reported on e-CRFs with those from source documents,
- authorizes direct access to source documents for monitoring, audits and inspections.

The trial-related documents must be retained as strictly confidential at the Investigator's site for a duration of 25 years or according to local requirements, after the completion or discontinuation of the trial.

15.3. END OF STUDY

15.3.1. Definition of the end of study

The end of the study is defined as the time point when all treated subjects will have either progressed or discontinued study treatments (including 30-day Safety Follow-Up visit) for any other reason (unacceptable toxicity, subject's decision, withdrawal of consent, initiation of subsequent anticancer therapy or death).

15.3.2. Supply of product after Main study period

After the Main study period (from first subject screened to 1 year after the start of study treatment of the last subject enrolled – 27 Dec 2020), access to study treatment will be provided through a Study extension period (from 28 Dec 2020) to all subjects whom the investigator considers are continuing to benefit from study treatment.

These subjects will receive treatment with encorafenib/binimetinib/cetuximab as long as they continue to demonstrate benefit and do not experience unacceptable toxicities and as long as none of the treatment discontinuation criteria are met or until binimetinib/encorafenib are commercially available in the first line setting of *BRAF*^{V600E} mutated mCRC or until the binimetinib/encorafenib development program is stopped (whichever comes first).

15.4. AUDIT

The purpose of a sponsor's audit, independent of and separate from monitoring or quality control activities, is to evaluate trial conduct and compliance with the protocol, sponsor's standard operating procedures, Good Clinical Practice, and the applicable regulatory requirements.

Audits may be conducted by the sponsor's Clinical Quality Assurance Department or delegate at each relevant location where activities dedicated to clinical trial are performed: for example at sponsor's site(s), at the investigational site(s), at CRO(s) site(s) and laboratory(ies) if applicable.

All study related documentation must be directly accessible to auditors.

The practical conditions for the audit are discussed between the auditees and the sponsor's Clinical Quality Assurance Department or their delegate.

15.5. INSPECTION

The relevant Health Authorities may inspect any investigational site or the Sponsor during the course of the study or after its completion, to verify the conduct of the study and quality of the data. The Investigator must provide direct access to the respective source documents.

15.6. CONFIDENTIALITY

The study materials (protocol, e-CRF, Investigator's brochures) contain confidential information. Except if agreed to in writing with the Sponsor, the Investigators must hold such information confidential, and must not disclose it to others (except where required by applicable law).

15.7. CLINICAL STUDY REPORT

Data analysis and CSR writing are the Sponsor's responsibility. Upon completion of the data analysis, a final report including a review of the objectives and methods, a presentation and discussion of the results are drawn up according to ICH Guidelines (Structure and Content of Clinical Study Reports, ICH-E3, CPMP/ICH/137/95).

The report is a clinical, (and) statistical, and pharmacokinetic integrated report. It must be signed by the sponsor's representative(s) and the coordinating Investigators.

15.8. STUDY RESULTS COMMUNICATION

Within a maximum period of 12 months after study completion global results of the research will be communicated to the Investigator.

According to the local regulations, subjects can ask the Investigator for the results.

If this study is part of a marketing authorisation application, its results will be published on the European Medicines Agency (EMA) website and on Pharmaceuticals and Medical Devices Agency

(PMDA) website (Japan). In that case, the documents will be anonymised to ensure data protection of individuals.

15.9. STUDY RESULTS PUBLICATION

The results of this study including data, reports, discoveries and inventions are the property of the Sponsor and are considered as confidential. Subject to any applicable laws in force, the Sponsor retains the right to be the first to publish or communicate the results of the study. In any case, no publication or communication relating to results of the study, in written or oral form, shall be made without Sponsor's prior written consent and shall comply with the following provisions:

- any communication or publication project must be provided to the Sponsor for review at least 60 days prior to the expected date of submission to the intended publisher or of planned presentation.

If requested by the Sponsor, the communication or publication project shall be withheld for an additional 60 days, to allow the filing of a patent application, or to allow the Sponsor to take any measures deemed appropriate to establish and preserve proprietary rights.

In case of a multicentric study, the Sponsor, in consultation with the SC, shall determine the author's list and order within the publication project according to their participation in the design of the protocol as well as their recruitment of eligible and analyzable subjects.

17. APPENDICES

17.1. RECOMMENDED GUIDELINES FOR THE MANAGEMENT OF CETUXIMAB-INDUCED, ENCORAFENIB-INDUCED AND/OR BINIMETINIB-INDUCED SKIN TOXICITY

Clinical judgment and experience of the treating physician should guide the management plan of each subject. In general, the following interventions are in addition to the cetuximab-induced rash and the encorafenib-induced and/or binimetinib-induced rash dosing guidelines provided (in **Section 1.2**).

The Initial Rash Treatment Regimen may be initiated as prophylactic treatment 24 hours prior to the first treatment, or later as needed to treat mild rash (NCI-CTCAE Grade 1).

Initial Rash Treatment Regimen:

- Application of topical agents to the most commonly affected skin areas such as face, scalp, neck, upper chest and upper back. Topical agents include the following:
 - Non-oily sunscreen (PABA-free, SPF \geq 30, UVA/UVB protection);
 - Topical steroids, preferably mometasone cream (e.g., Elocon[®]);
 - Topical erythromycin (e.g., Eryaknen[®]);
 - Topical pimocrolimus.

Note: Topical agents should be applied on a daily basis starting on Day 1 of study treatment or 24 hours prior to first treatment, and more often as needed.

- Possibly oral doxycycline (100 mg daily) for the first 2 to 3 weeks of study drug administration.

Other effective medications are antihistamines, other topical corticosteroids, other topical antibiotics and low-dose systemic corticosteroids.

The treatment algorithm based on NCI-CTCAE grade is as follows:

Mild Rash (CTCAE Grade 1) Treatment Regimen:

- Initiate Initial Rash Treatment Regimen, if not already started.
- Use of topical corticosteroid (e.g., mometasone cream) and/or topical antibiotic (e.g., erythromycin 2%) is recommended.
- The subject should be reassessed within a maximum of 2 weeks, or as per Investigator opinion.

Moderate Rash (CTCAE Grade 2) Treatment Regimen:

- Use of topical erythromycin or clindamycin (1%) plus topical mometasone or topical pimecrolimus (1% cream) plus oral antibiotics, such as lymecycline (408 mg QD), doxycycline (100 mg BID) or minocycline (50 to 100 mg BID).
- Although there has been no evidence of phototoxicity or photosensitivity in subjects treated with binimetinib, doxycycline (or minocycline as second-line) should be used with thorough UV protection (i.e., avoidance of direct exposure to sunlight, use of sunscreen and sunglasses, etc.).
- Use of acitretin is not recommended.

Severe Rash (CTCAE Grade 3-4) Treatment Regimen:

CTCAE Grade 3:

- In addition to the interventions recommended for moderate rash, consider oral prednisolone at a dose of 0.5 mg/kg. Upon improvement, taper the dose in a stepwise manner (25 mg for 7 days, subsequently decreasing the dose by 5 mg/day every day).
- Alternatively, in addition to the interventions recommended for moderate rash, consider oral isotretinoin (low dose, i.e., 0.3 to 0.5 mg/kg) (**Kopetz S et al, 2017; Lacouture ME et al, 2011**)
- Use of acitretin is not recommended.

CTCAE Grade 4 Treatment Regimen:

- Immediately discontinue the subject from study drug and treat the subject with oral or topical medications (see recommendation CTCAE Grade 3).

Symptomatic Treatment Regimen:

It is strongly recommended that subjects who develop rash/skin toxicities receive symptomatic treatment:

- For pruritic lesions: use cool compresses and oral antihistamine agents.
- For fissuring: use Monsel's solution, silver nitrate or zinc oxide cream. If not sufficient, use mild corticosteroid ointments or ointments containing a combination of corticosteroid and antibiotic such as Fucicort®.
- For desquamation: use emollients that are mild pH 5/neutral (recommended to contain 10% urea).
- For paronychia: use antiseptic bath and local potent corticosteroids, use oral antibiotics, and, if no improvement is seen, refer to a dermatologist or surgeon.
- For infected lesions: obtain bacterial and fungal cultures and treat with topical or systemic antibiotics, if indicated, based on sensitivity of culture.

17.2. RECOMMENDED GUIDELINES FOR THE MANAGEMENT OF ENCORAFENIB-INDUCED HAND-FOOT SKIN REACTIONS (HFSR)

Clinical judgment and experience of the treating physician should guide the management plan of each subject. In addition to the HFSR dosing guidelines in the protocol, the following algorithm is recommended for the management of HFSR based on the severity (CTCAE grading,) of HFSR (adapted from **Nardone B et al, 2012**). HFSR (adapted from **Nardone B et al, 2012**).

Algorithm for the Management of HFSR Based on the Severity of HFSR

HFSR severity	Intervention
No HFSR	Maintain Frequent Contact with physician to ensure early diagnosis of HFSR
Therapy initiation	Full body-skin examination, pedicure, evaluation by podiatrist or orthotist; wear thick cotton gloves and/or socks; avoid hot water, constrictive footwear and excessive friction
	If symptoms develop, proceed to next step
	
Grade 1	Maintain current dose of BRAF inhibitor; monitor subject for change in severity
Minimal skin changes or dermatitis without pain e.g.: 
 • Numbness • Tingling • Dysesthesia • Paresthesia • Erythema • Edema • Hyperkeratosis No interference with ADL	Avoid hot water; use moisturizing cream for relief; wear thick cotton gloves and/or socks; use a 20-40% urea , salicylic acid 3-6%; ammonium lactate 12 % or lactic acid 12 % based creams to aid exfoliation.
	If symptoms worsen, proceed to next steps
	
Grade 2	Maintain current dose of BRAF inhibitor; monitor subject for change in severity
Skin changes with pain e.g. Peeling 
 • Blisters • Bleeding • Edema • Hyperkeratosis Limited instrumental ADL	Treat as with Grade 1 toxicity, with the following additions: clobetasol 0.05% ointment, 2-4% lidocaine, opiates, NSAIDS, or GABA agonists for pain; follow dose modifications listed in Table 14
	If no improvement within 15 days, proceed to next steps.

	
Grade 3	Interrupt dose until improvement to Grade 0-1
Severe skin changes with pain e.g. Peeling 
 • Blisters • Bleeding • Edema • Hyperkeratosis Limiting self-care ADL	Treat as for Grades 1 and 2 Follow dose modifications listed in Table 14

The following supportive care measures for the prevention, and/or management of HFSR summarized in the table below should be instituted along with proper subject education.

Supportive Care for the Prevention and Management of HFSR

Stage	Recommendations
Prior to initiation of study treatment	Educate the subject about the early signs and symptoms of HFSR and discuss the importance of early reporting. HFSR could start as early as 2-5 days after study drug initiation, and mostly expected to occur during the first 2 months of treatment.
Prevention of HFSR for the first 2 months of treatment with encorafenib	Monitor the subject for signs and symptoms of HFSR. Instruct the subject to: 
 - Apply emollient cream regularly to hands and feet: use 20-40% urea , salicylic acid 3-6%; ammonium lactate 12% or lactic acid 12 % based creams - Wear cotton socks or gloves to bed to enhance the absorption of creams - Avoid tight, irritating or ill-fitting clothing and shoes - Avoid repetitive activity or staying in one position for long periods of time - Pat (do not rub) skin dry with towels - Avoid extremes of temperature, pressure and friction - Avoid performing mechanically stressful manual work - Cushioning of callused areas - Use of moisturizing and keratolytic creams to control existing palmar and plantar hyperkeratosis
Treatment of HFSR	1) Ensure that subject follows treatment interruption or dosage reduction guidelines 2) Monitor the subject for worsening/resolution of HFSR (Normal frequency monthly, except if subject has Grade 2 or 3 HFSR, where bi weekly- visits are recommended) 3) Prescribe analgesics if necessary 4) Instruct the subject to: 
 - Continue the use of prevention strategies - Cushion sore skin - For control or relief of pain symptoms, subject may submerge hands and feet in cool water baths or apply cold compresses for relief
^a Wear loose-fitting clothing made of soft, natural fabrics and shoes that are wide and comfortable. Avoid tight belts, panties and bras. This table is adapted from (VonMoos et al, 2008).	

17.3. RECOMMENDED GUIDELINES FOR THE MANAGEMENT OF BINIMETINIB-INDUCED DIARRHEA

Proactively Investigate for Occurrence of Diarrhea and Educate Subject:

1. Remind subjects at each visit to contact the Investigator immediately upon the first sign of loose stool or symptoms of abdominal pain. Additionally, at each study visit, each subject should be asked regarding occurrence of diarrhea or diarrhea-related symptoms. If the subject has had symptoms, the subject should be asked regarding the actions taken for these symptoms and re-instruct if indicated.
2. Subjects should be instructed on dietary modification and early warning signs of diarrhea and potentially life-threatening illnesses (e.g., severe cramping might be a sign of severe diarrhea; fever with diarrhea might be a sign of infection; fever and dizziness on standing might be a sign of shock).
3. Subjects should be educated about what to report to the Investigator (i.e., number of stools, stool composition, stool volume).

Anti-Diarrhea Therapy:

In order to effectively manage diarrhea and mitigate the escalation in severity or duration of diarrhea, subject education as outlined above, as well as proper management of diarrhea is important.

Management of diarrhea should be instituted at the first sign of abdominal cramping, loose stools or overt diarrhea. All concomitant therapies /used for treatment of diarrhea must be recorded on the e-CRF. It is recommended that subjects be provided loperamide tablets and be instructed on the use of loperamide on the first day of binimetinib dosing. In addition to the binimetinib-induced diarrhea dosing guidelines provided in **Table 14** of the protocol, these instructions should be provided at each visit and the site should ensure that the subject understood the instructions.

See **Section 7** in the protocol to explain the frequency of diarrhea and its relationship to NCI-CTCAE, v.4.03 grading and to determine if diarrhea is complicated or uncomplicated.

Rule out Other or Concomitant Causes:

These may include:

- Infection with *Candida*, *Salmonella*, *Clostridium difficile*, *Campylobacter*, *Giardia*, *Entamoeba* or *Cryptosporidium* species, which can lead to severe infections in immunosuppressed subjects.
- Medication-induced diarrhea.
- Malabsorption/lactose intolerance.
- Fecal impaction, partial bowel obstruction.

For Uncomplicated Grade 1/2 Diarrhea:

- Stop all lactose-containing products and alcohol, and eat frequent small meals that include bananas, rice, applesauce or toast.
- Stop laxatives, bulk fiber (e.g., Metamucil[®]), and stool softeners (e.g., docusate sodium, Colace[®]).
- Stop high-osmolar food supplements (e.g., Ensure[®] Plus, Jevity[®] Plus [with fiber]).
- Drink 8 to 10 large glasses of clear liquids per day (e.g., water, Pedialyte[®], Gatorade[®], broth).
- Consider administration of a standard dose of loperamide: initial administration 4 mg, then 2 mg every 4 hours (maximum of 16 mg/day) or after each unformed stool.
- Discontinue loperamide after 12-hours diarrhea-free (Grade 0) interval.
- Consider temporary interruption of binimetinib until resolved to Grade \leq 1. Re-treatment may then be resumed at current dose level.
- If uncomplicated Grade 1 to Grade 2 diarrhea persists for more than 24 hours, escalate to high-dose loperamide: 2 mg every 2 hours (maximum of 16 mg/day) or after each unformed stool.

Note: Oral antibiotics may be started as prophylaxis for infections under the discretion of the physician.

- If uncomplicated Grade 1 to Grade 2 diarrhea persists after 48 hours of treatment with loperamide, discontinue loperamide and begin a second-line agent which can be an opiate (opium tincture or paregoric), octreotide acetate or steroid (budesonide).

For Complicated Grade 1/2 Diarrhea or Any Grade 3/4 Diarrhea:

- The subject must call the Investigator immediately.
- Temporarily interrupt binimetinib treatment until resolved to Grade \leq 1. Restart binimetinib at a reduced dose level.
- If loperamide has not been initiated, initiate loperamide immediately. Initial administration 4 mg, then 2 mg every 4 hours (maximum of 16 mg/day) or after each unformed stool.
- Administer IV fluids and electrolytes as needed. In case of severe hydration, replace loperamide with octreotide acetate.
- Monitor/continue IV fluids and antibiotics as needed. Intervention should be continued until the subject is diarrhea-free for at least 24 hours.
- Hospitalization may need to be considered.

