Uveitis should be graded according to NCI-CTCAE, v.4.03 as described in **Table 11**, Hand-foot skin reactions (HFSR) should be graded according to NCI-CTCAE, v.4.03 as described in **Table 12**. Diarrhea should be graded according to modified NCI-CTCAE, v.4.03 as described in **Table 13**. Furthermore, please refer to **Section 17.1** for additional supportive care recommended guidelines for the management of: cetuximab-induced, encorafenib-induced and/or binimetinib-induced skin reaction (**Section 17.1**), encorafenib-induced HFSR (**Section 17.2**), binimetinib-induced diarrhea (**Section 17.3**) and binimetinib-associated interstitial lung disease/pneumonitis (**Section 17.7**).

Table 9: Modified NCI CTCAE, Version 4.03 Grading of Eye Disorders

Grade	Description
1	Asymptomatic or mild symptoms; clinical or diagnostic observations only; intervention not indicated
2	Moderate; minimal, local or noninvasive intervention indicated; limiting age-appropriate instrumental activities of daily living
3	Severe or medically significant but not immediately sight threatening; hospitalization or prolongation of existing hospitalization indicated; disabling; limiting self-care activities of daily living
4	Sight-threatening consequences; urgent intervention indicated; blindness (20/200 or worse) in the affected eye

Table 10: NCI CTCAE, Version 4.03 Grading of Serous Detachment of the Retina

Grade	Description
1	Asymptomatic (but with findings in ocular coherence tomography, fundoscopy and/or slit lamp biomicroscopy)
2	Symptomatic with moderate decrease in visual acuity (20/40 ^a or better); limiting instrumental activities of daily living
3	Symptomatic with marked decrease in visual acuity (worse than 20/40 ^a); limiting self-care activities of daily living
4	Blindness (20/200a or worse) in the affected eye

Note: For rhegmatogenous retinal detachment, grade according to NCI-CTCAE v.4.03 Retinal Detachment. a Please refer to (**Section 17.3**).

Table 11: NCI CTCAE, Version 4.03 Grading of Uveitis

Grade	Description
1	Asymptomatic; clinical or diagnostic observations only
2	Anterior uveitis; medical intervention indicated
3	Posterior or pan-uveitis
4	Blindness (20/200 ^a or worse) in the affected eye

a Please refer to (**Section 17.3**).

Table 12: NCI CTCAE, Version 4.03 Grading of Hand-foot Skin Reaction (HFSR)^a

Grade	Description ^b

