1	Minimal skin changes or dermatitis (e.g., erythema, edema, numbness, dysesthesia, paresthesia, tingling or hyperkeratosis) without pain
2	Skin changes (e.g., peeling, blisters, bleeding, edema, or hyperkeratosis) with pain; limiting instrumental ADL
3	Severe skin changes (e.g., peeling, ulceration, blisters, bleeding, edema, or hyperkeratosis) with pain; limiting self-care ADL

Abbreviations: ADL=activities of daily living.

a. HFSR or palmar-plantar erythrodysesthesia syndrome, a disorder characterized by redness, marked discomfort, swelling, and tingling in the palms of the hands or the soles of the feet;

b. More specific examples for Grade 1 and Grade 3 are added to facilitate proper grading (from the sorafenib package insert; West Haven, CT: Bayer Pharmaceuticals Corporation; 2007).

Table 13: Modified NCI CTCAE, Version 4.03 Grading of Diarrhea

Grade	Description
1	Increase of < 4 stools per day over Baseline; mild increase in ostomy output compared to Baseline
2	Increase of 4-6 stools per day over Baseline; moderate increase in ostomy output compared to Baseline
1/2 complicated	Definition as above (Grade 1/2) with the following complicating signs/symptoms: 
 • Moderate to severe cramping • Grade ≥ 2 nausea/vomiting • Decreased performance status • Fever • Sepsis • Neutropenia • Frank bleeding • Dehydration

Grade	Description
	
 Unresolved diarrhea after 48 hours of treatment with loperamide (including high-dose administration) and initiation of second-line treatment
3	Increase of ≥ 7 stools per day over Baseline; incontinence; hospitalization indicated; severe increase in ostomy output compared to Baseline; limiting self-care activities of daily living
4	Life threatening consequences; urgent intervention indicated

Table 14: Recommended dose modifications for Encorafenib-related and/or Binimetinib related AEs

Worst toxicity CTCAE, v.4.03 Grade (unless otherwise specified ^a)	Dose Modification for Encorafenib and for Binimetinib
Eye Disorders - Retinal Events (including serous detachment of the retina), Note: Results and images of ocular coherence tomography (OCT) must be made available upon request. Any visual acuity impairment at screening should be documented and should be considered as baseline.	

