Uncomplicated Grade 1-2	Maintain dose of encorafenib. Consider temporary interruption of binimetinib until resolved to Grade ≤ 1. Then resume treatment at current dose level of binimetinib.
Complicated Grade 1-2	Consider temporary interruption of encorafenib until resolved to Grade ≤ 1. Then resume treatment at current dose level of encorafenib Interrupt dosing of binimetinib until resolved to Grade ≤ 1. Then resume treatment at 1 reduced dose level ^b of binimetinib.
Grade 3-4	Interrupt dosing of encorafenib and binimetinib until resolved to Grade ≤ 1. Then resume treatment at current dose level of encorafenib if, in the judgment of the Investigator, the toxicity is considered to be unrelated to encorafenib, or at one reduced dose level ^b . Resume treatment at 1 reduced dose level ^b of binimetinib.
Nausea/Vomiting	
Grade 1-2	Maintain dose level of encorafenib and binimetinib. Promptly institute antiemetic measure.
Grade 3	Interrupt dosing of encorafenib and binimetinib until resolved to Grade ≤ 1. Then resume treatment at 1 reduced dose level ^b of encorafenib. Resume treatment with binimetinib at the current dose if, in the judgment of the Investigator, the toxicity is considered to be unrelated to binimetinib, or at 1 reduced dose level ^b . Note: Interrupt dosing of encorafenib and binimetinib for ≥ Grade 3 vomiting or Grade 3 nausea only if the vomiting or nausea cannot be controlled with optimal antiemetics (as per local practice).
Grade 4	Permanently discontinue encorafenib and binimetinib ^f .
Interstitial lung disease/pneumonitis - Section 17.7	
Grade 1	Maintain dose level of encorafenib and binimetinib. Monitor weekly.
Grade 2	Maintain dose of encorafenib. Withhold binimetinib for up to 3 weeks. If improved to Grade 0 or 1, resume treatment at 1 reduced dose level of binimetinib. If not resolved within 3 weeks, permanently discontinue binimetinib.
Grade 3-4	Permanently discontinue binimetinib.
All Other Adverse Events (Suspected To Be Related To Encorafenib and/or Binimetinib)	
Grade 1-2	If the event is a persistent Grade 2 AE not responsive to a specific therapy, consider interruption or reduction of encorafenib and binimetinib, as applicable
Grade 3	Interrupt dosing of encorafenib and binimetinib until resolved to Grade ≤ 1 or to pretreatment/baseline level. If the event resolves ≤ 21 days, then study drug may be resumed at 1 reduced dose level ^b based upon the Investigator's discretion.

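### Grade 1/2 diarrhoea unresolved after 48 hours of loperamide, with second-line treatment started, is complicated in Table 13 but stays in the uncomplicated branch of Section 17.3, and the label decides the binimetinib instruction

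*Protocol*

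**What the plan says.** Section 6.5.4.1 of the protocol names the grading source: "Diarrhea should be graded according to modified NCI-CTCAE, v.4.03 as described in" Table 13. That table has a category between Grades 2 and 3, introduced as "Definition as above (Grade 1/2) with the following complicating signs/symptoms". The last item in its list is "Unresolved diarrhea after 48 hours of treatment with loperamide (including high-dose administration) and initiation of second-line treatment".

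Table 14 gives the dosing consequence. For uncomplicated Grade 1-2 diarrhoea, encorafenib is maintained, a temporary binimetinib interruption is to be considered, and binimetinib resumes at the current level. For complicated Grade 1-2 diarrhoea, an encorafenib interruption is to be considered, and the binimetinib instruction is "Interrupt dosing of binimetinib until resolved to Grade ≤ 1. Then resume treatment at 1 reduced dose level".

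Section 17.3 repeats the two-way split. Under "For Uncomplicated Grade 1/2 Diarrhea" it lists dietary measures and standard loperamide, and then the binimetinib step: "Consider temporary interruption of binimetinib until resolved to Grade \leq 1. Re-treatment may then be resumed at current dose level". Next comes an increase in loperamide if the diarrhoea lasts more than 24 hours. The branch closes with "If uncomplicated Grade 1 to Grade 2 diarrhea persists after 48 hours of treatment with loperamide, discontinue loperamide and begin a second-line agent". The other branch, for complicated Grade 1/2 or any Grade 3/4 diarrhoea, has binimetinib interrupted and restarted at a reduced level.

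To tell complicated from uncomplicated, Section 17.3 refers the reader to Section 7 of the protocol.

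**The concern.** The state that Table 13 uses to define complicated diarrhoea is the state reached at the end of Section 17.3's uncomplicated branch. Section 17.3 still calls the event uncomplicated at that step and does not tell the site to change branch. The binimetinib instruction follows the label, so two sites with the same subject could interrupt and reduce binimetinib in one case and continue or resume at the current level in the other.

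Three things are at stake: consistent dosing and safety management of subjects with persistent diarrhoea, the descriptive exposure results, and the counts of adverse events that lead to dose reduction or interruption. SAP Section 15.1 summarises dose reductions, interruptions and relative dose intensity for each drug. SAP Section 15.2 tabulates adverse events leading to dose reduction and to interruption by study drug. Diarrhoea was the most frequent event in the triplet safety lead-in (protocol Table 6: 23 of 30 subjects, any grade), so the rule will be consulted often.

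**Working it through.** The plan has no figure to reproduce here. The check is a comparison of texts, followed by a short calculation for scale.

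**1. Do the two texts describe the same state?**

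| Element | Table 13, complicated item | Section 17.3, last step of the uncomplicated branch |
|---|---|---|
| Severity | Grade 1/2 | Grade 1 to 2 |
| Duration | Unresolved after 48 h of loperamide | Persists after 48 h of loperamide |
| Loperamide | High-dose use included | High-dose step already taken, after 24 h |
| Second-line treatment | Started | To be started at this step |
| Label | Complicated | Uncomplicated |

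Table 13 requires both persistence and the start of second-line treatment. Persistence alone is not enough. Section 17.3 starts second-line treatment at the same 48-hour point, so a subject for whom the step has been carried out meets both parts of the Table 13 item.

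**2. Does the label matter?** Yes, and Table 14 and Section 17.3 agree on the binimetinib consequence.

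- Uncomplicated: interruption to be considered, current level on resumption.
- Complicated: interruption, reduced level on resumption.

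Table 14 also gives different encorafenib wording for the two labels. In Section 17.3 only the complicated branch has the subject call the investigator at once and mentions intravenous fluids.

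**3. Can the site settle it by cross-reference?** Section 17.3 points to Section 7, which covers concomitant therapy and holds no definition of complicated diarrhoea. Section 7.2.3 points back to Section 17.3. The definition is in Table 13, in Section 6.5.4.1.

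**4. Scale for one subject.** Inputs: protocol Table 8 (binimetinib starting dose 45 mg BID, level -1 30 mg BID) and SAP Section 15.1 (planned dose intensity 90 mg/day).

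- Current level: 2 × 45 = 90 mg/day; 100 × 90/90 = 100% of planned dose intensity on those days.
- One level down: 2 × 30 = 60 mg/day; 100 × 60/90 = 66.7%.

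This holds for the days after resumption, for a subject at the starting dose, until any re-escalation. The effect on relative dose intensity over the whole treatment depends on how long the lower level lasts, and the documents do not allow that to be computed.

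**The case against.** The strongest reply is that the protocol can be read in sequence. Section 6.5.4 says that doses should be modified as set out in Tables 14 and 15 and on the basis of the worst preceding toxicity. Section 6.5.4.1 makes Table 13 the grading source. Section 17.3 presents itself as an addition to the Table 14 dosing guidance. On that reading the event is uncomplicated up to 48 hours and becomes complicated once second-line treatment starts, so the adjective in Section 17.3 is correct at the moment the step is taken. Section 17.3 also attaches no binimetinib instruction to the 48-hour step itself; its current-level instruction appears earlier in the same branch.

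Much of this stands. A careful site that reads all these sections can reach one answer, so a reader should not infer that the protocol imposes two irreconcilable doses on the same subject. The sequence is nevertheless an inference: Section 17.3 never states the change of category and misdirects the reader who looks for the definition. Its only step for replacing loperamide after 48 hours without resolution is in the uncomplicated branch. The complicated branch tells sites to start loperamide if it has not been started, and to replace it in a stated hydration situation.

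The wording is also softer than a mandate. Table 14 and Section 17.3 are both headed as recommendations, and Section 7.2.3 allows institutional guidelines or local prescribing information for treating diarrhoea. Section 6.5.4.1 permits re-escalation, at the investigator's discretion, once the event has returned to baseline and been stable for at least 14 days, with no limit on the number of times. A lower level may therefore be temporary.

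A reader might also see a conflict in the loperamide step, "escalate to high-dose loperamide: 2 mg every 2 hours (maximum of 16 mg/day", because twelve 2 mg doses in 24 hours would total 24 mg. The documents do not support that: the stated maximum caps the interval schedule and does not contradict it.

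**Conclusion.** The inconsistency is real and limited. The same clinical state is labelled complicated in Table 13 and is reached under the uncomplicated heading in Section 17.3. No transition is stated, and the pointer to the definition is wrong. A site following Section 17.3 alone would stay on the branch with optional interruption and the current dose level. A site following Tables 13 and 14 would interrupt and reduce.

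For a subject at the starting dose the difference after resumption is 90 versus 60 mg/day, or 100% versus 66.7% of planned dose intensity on those days, subject to possible re-escalation. How many subjects this touches is unknown. It is tempting to take the share of the lead-in whose worst diarrhoea was Grade 1-2, (23 - 1)/30 = 73%, as the size of the problem. That is only a ceiling, from 30 previously treated subjects. The relevant group is those whose diarrhoea is unresolved after 48 hours of loperamide and who start second-line treatment, and the documents give no figure for it.

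The point bears on subject dosing and safety management, and on between-site variation in binimetinib interruptions, dose reductions and relative dose intensity. It does not affect the test of the confirmed response rate or the sample size. Nothing here says which dosing instruction is right. The conclusion assumes that some sites use Section 17.3 as their working guide to diarrhoea without tracing the event back to Table 13.

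**What to change.** Reconcile Table 13, Table 14 and Section 17.3 so that Grade 1/2 diarrhoea unresolved after 48 hours of loperamide, with second-line treatment started, falls in one category with one binimetinib instruction. If a change of category at the start of second-line treatment is intended, Section 17.3 should state it at that step. Replace the reference to Section 7 in Section 17.3 with a reference to Table 13. Which category and which instruction apply is for the sponsor's clinical team to decide.

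The cost is a few lines of wording in the appendix and, if needed, in the tables. The sample size, the analyses and the data collected do not change.
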